5 INTRODUCTION

This Statistical Analysis Plan (SAP) provides details of specific planned analyses to be performed on the data to be collected from clinical trial BT – L-CsA – 301 – SLT (BOSTON-1). This SAP is based on the Clinical trial protocol version 5.0 (amendment 4.0), dated 13 April 2023.

Modifications to this SAP will be subject to detailed documentation relating to timing and rationale, with a focus on identifying and providing a rationale for changes. Any deviations from the SAP will be fully described in the integrated clinical study report (CSR).

The main purpose of this SAP is to pre-specify statistical analyses that relate to identified clinical trial objectives. Any supportive **CCI** analyses presented in the integrated CSR which are not described in the SAP will be noted as such.

6 TRIAL OBJECTIVES

The objective of this trial is to assess the efficacy and safety of add-on aerosolized Liposomal Cyclosporine A Inhalation Solution (L-CsA) to Standard of Care (SoC) therapy as compared to SoC therapy alone in the treatment of bronchiolitis obliterans syndrome (BOS) in single lung transplant (SLT) recipients.

7 INVESTIGATIONAL PLAN

7.1 Trial Design

This is a Phase III, prospective, multicenter, randomized, controlled clinical trial of L-CsA for the treatment of BOS in adults with clinically defined BOS (Chronic Lung Allograft Dysfunction (CLAD) – BOS phenotype) following SLT. Patients will receive either L-CsA (5 mg) via the **CCI** SoC treatment or SoC alone, for a period of 48 weeks. All patients will be eligible to continue in an open-label extension trial of L-CsA, BT – L-CsA – 303 – FU (BOSTON-3) following completion of BOSTON-1.

A total of 11 visits (Screening, V1 through V10) will be performed during the clinical trial. After informed consent has been obtained, a Screening Visit will be carried out in order to check general eligibility for participation. If a patient fails the screening process due to not meeting inclusion/exclusion criteria, a re-screening is allowed. At the Baseline Visit (V1, randomization visit), inclusion and exclusion criteria will be re-checked, and baseline serial spirometry will be performed. During the 48-week treatment period, visits are scheduled every 4-8 weeks (V2, ..., V9). Visit 9 (End of Treatment, EoT) is scheduled to occur 48 weeks after Visit 1. If a patient has an event that meets one of the criteria for progression of BOS, progression of BOS must be

confirmed by measurements that are taken with CCI [REDACTED] spirometer at least 2 weeks apart. Visit 10 (End of Study, EoS) is a safety follow-up visit performed 4 weeks after Visit 9/EoT only in patients not rolling over to the extension study (BOSTON-3) or if possible, in patients who decided to withdraw the consent during the study. For patients who will enroll to BOSTON-3, the EoT visit will be the EoS visit.

However, if one of the visits from Visit 2 to Visit 8 and discontinuation visits cannot be performed at site due to COVID-19, remote visits (e.g., by telephone) are possible.

7.2 Randomization and Stratification

At the Baseline visit (V1), after all inclusion and exclusion criteria have been fully evaluated, eligible patients will be randomized with equal probability to one of two treatment arms, a control arm (SoC alone) and an investigational arm (L-CsA plus SoC). The investigational medicinal product (IMP) is L-CsA. To assure balance between treatment arms with regard to key variables and potential confounders, stratification prior to randomization will be performed for the following variables:

- Screening FEV₁ ≥81% of personal best FEV₁ value post-transplant versus Screening FEV₁ between 80-51% of personal best FEV₁ value post-transplant
- Underlying indication for lung transplant: Chronic obstructive pulmonary disease (COPD) versus all other underlying diseases
- Region: North America versus all other countries together

Within each of the 8 strata, patients will be randomly assigned with equal probability (1:1) to either the investigational or control arm using a permuted blocks randomization. The randomization code, including specification of the block size, will be generated by a statistician not otherwise involved with the trial, using validated software. The unique randomization number and treatment assignment of each patient will be provided to the Investigator through the electronic Case Report Form (eCRF) after eligibility has been verified. The number assigned to a patient will be that patient's unique identifier throughout the clinical trial and cannot be re-assigned to another patient.

This is an open-label clinical trial. Clinical trial monitors, treating physicians, study nurses, study coordinators, and enrolled patients will not be blinded to treatment assignment.

7.3 Primary Efficacy Endpoint

- Mean change in FEV₁ (L) from baseline to Week 48

FEV₁ data collected from the on site CCI [REDACTED] spirometer will be considered primary, while the data collected with the CCI [REDACTED] home spirometer will be used for supportive analyses.

L-CsA:

Treatment of BOS after SLT

Protocol Number:

BT – L-CsA – 301 – SLT

Sponsor:

Zambon SpA

7.6 Safety Endpoints

- Adverse events (AEs) (including infections and malignancies)
- Acute tolerability of IMP (L-CsA)
- Clinical laboratory variables
- Renal function
- Vitals signs
- Physical examinations

8 STATISTICAL CONSIDERATIONS

8.1 General Considerations and Descriptive Statistics

All report outputs will be produced using [REDACTED] version 9.2 or later, in a secure and validated environment. All tables, figures and data listings (TFLs) to be included in the report will be independently checked for consistency and integrity.

The data recorded in the eCRF will be summarized as appropriate, per treatment group and for the total group, using the following descriptive measures:

- All continuous variables will be summarized using descriptive statistics (i.e., n, mean, standard deviation (SD), median, Q1, Q3, minimum, and maximum).
- All categorical variables will be summarized by using frequency counts and percentages.
- Discrete ordinal or higher-level data will be summarized as continuous data, but a tabulation of categories may also be included, depending on the number of categories.
- For time-to-event variables, cumulative event-free survival times will be evaluated using the Kaplan-Meier method. A frequency table showing the number of events and censored patients by treatment group, will be presented along with the event-free rates (and two-sided 95% confidence). Kaplan-Meier graphs will be presented along with the number of patient-at-risk at exact time points. If different rules are not specified, patients who are free from event will be censored at the study termination.

For all measures analyzed descriptively (i.e., measures to characterize the treatment groups and their baseline status, efficacy, and safety outcomes), tabulations comparing the treatment groups will be prepared. For outcomes measured more than once, the analyses will include tabulations of the measured values by visit, as well as change from baseline. Where provided, all confidence intervals will be two-sided 95% intervals.

8.1.1 Baseline Definition

CCI [REDACTED] baseline FEV₁: the FEV₁ value that is the mean of the best FEV₁ obtained with the CCI [REDACTED] study spirometer at the Screening Visit and the pre-randomization best FEV₁ obtained at the Baseline Visit (V1) is referred to as “baseline FEV₁”. If the value at Screening visit is missing, then the baseline FEV₁ will be the pre-randomization value from the Baseline Visit (V1). If the pre-randomization value at Baseline Visit (V1) is missing, then the baseline FEV₁ will be the value from the Screening Visit.

Other CCI [REDACTED] baseline spirometry values: will be defined similarly as for Baseline FEV₁.

CCI [REDACTED] baseline FEV₁: will be defined similarly as for CCI [REDACTED] baseline FEV₁ but using the CCI [REDACTED] home spirometer.

L-CsA:
Treatment of BOS after SLT

Protocol Number:
BT – L-CsA – 301 – SLT

Sponsor:
Zambon SpA

Baseline laboratory values: the last measurement obtained prior to or at the Baseline Visit at V1.

Other baseline measurements: unless otherwise specified, baseline refers to measurement obtained at the Baseline Visit at V1.

8.1.2 Treatment Definition

Treatment refers to add-on L-CsA to SoC therapy, as well as SoC therapy alone.

8.2 Sample Size Considerations

The initial sample size was based on the following considerations. Assuming a treatment group difference for mean FEV₁ change from baseline of 200 mL (0.2 L) and a standard deviation of 350 mL (0.35 L) at the end of treatment Week 48, an independent samples t-test with a one-sided type I error level of $\alpha=0.025$ will have at least 80% power to reject the null hypothesis when the sample size in each treatment group is at least 50 patients. To compensate for a loss of power due to premature withdrawals, a total of 110 patients were initially planned to be randomized.

In accordance with the amended version of the protocol (version 5.0) and following Food and Drug Administration **CCI** [REDACTED]

[REDACTED]
[REDACTED]
[REDACTED]
[REDACTED].

It was anticipated that approximately 160-170 patients have been randomized in BOSTON-2 and approximately 60 patients in BOSTON-1. 169 patients were actually randomized in BOSTON-2 and 62 patients in BOSTON-1.

8.3 Interim Analysis

Due to premature stop of enrollment **CCI** [REDACTED]

[REDACTED] the originally pre-planned interim analysis for sample size re-estimation was deemed unnecessary and it will not be performed.

8.4 Data Monitoring Committee and Confidentiality of Results

An independent Data Monitoring Committee (DMC) will be established to monitor the safety of the IMP throughout the conduct of BOSTON-1 and BOSTON-2 studies. The DMC will monitor safety by evaluating the safety analysis generated by the unblinded independent statistician during the course of the clinical trial. Details of the safety analyses will be included in the DMC's Charter (from **CCI** [REDACTED]). The DMC will evaluate the treatment groups for possible trends

L-CsA:
Treatment of BOS after SLT

Protocol Number:
BT – L-CsA – 301 – SLT

Sponsor:
Zambon SpA

in AEs, determine whether the basic clinical trial assumptions remain valid, evaluate whether the overall integrity, scientific merit and conduct of the clinical trials remain acceptable, and make recommendations to the Sponsor.

The DMC will perform a comparison between the rate of observed COVID-19 cases, rate of patients' withdrawal, and rate of missing data among trial participants in both treatment arms.

Members of the DMC will be unblinded to the treatment group label, i.e., the DMC will know which group is L-CsA + Standard of Care and which group is Standard of Care alone. The DMC will evaluate all safety and acute tolerability parameters, to be detailed in the DMC charter.

Safety and acute tolerability parameters include AEs, acute tolerability of L-CsA, infections, malignancies, clinical laboratory data (white blood cell count with differential, red blood cell count, platelet count, alkaline phosphatase, alanine aminotransferase, aspartate aminotransferase, gamma glutamyl transferase (γ -GT), blood urea nitrogen, serum bilirubin, serum creatinine), vital signs, physical examinations and FEV₁. The statistics provided will be merely descriptive.

Criteria for membership, responsibilities, meeting frequency, and identification of data listings, summaries and analyses to be provided to the DMC are detailed in the DMC charter.

Statistical analyses to be provided to DMC are planned in a specific DMC SAP.

8.5 Adjudication Committee

The adjudication committee (AC) – consisting of three independent physicians, with documented expertise in the clinical management of lung transplantation and diagnosis and treatment of BOS - will maintain the role of reviewing the BOS progression data in blind condition once each participating patient completes the study period, with the aim to ensure consistent and complete recording of data. If necessary, the AC may query the sites to ask for clarifications. In case there are discrepancies between the assessment of the AC and that of the investigator regarding BOS progression events, the CRO will notify the investigator. In all cases, the final decision as to whether or not specific event qualifies as BOS progression stands with the Investigator.

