#### 9.3.1 Blinding

The pulmonary function technicians, respiratory therapists, or physiotherapists who conduct spirometry on site will be blinded to treatment assignment. Patients and other unblinded personnel will be asked to not share treatment assignment information with the pulmonary function technicians, respiratory therapists, and physiotherapists. For details of the blinding of the Data Monitoring Committee members, see [Section 13.2](#). For details of the blinding of the Adjudication Committee members, see [Section 13.3](#). Clinical trial monitors, treating physicians, study nurses, study coordinators, and enrolled patients will not be blinded to treatment assignment.

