#### 12.1.2 Progression of BOS

Due to the patchy distribution of affected areas in the pulmonary allograft, chronic rejection and BOS are not uniformly detectable by biopsy. This method has turned out to be too unspecific and harmful for routine diagnostic use. Therefore, non-invasive spirometry has been routinely

---

established using standardized airflow measurements which nowadays is used to determine FEV1 as a surrogate marker for the diagnosis of BOS, its classification and its control of progression.

Progression of BOS during the treatment period is defined as a decline of FEV1 of  $\geq 10\%$  or  $\geq 200$  mL from Baseline FEV1 and absolute decrease in FEV1/FVC of  $> 5\%$  that is confirmed by measurements that are taken with **CCl** spirometer at least 2 weeks apart OR worsening in BOS Severity grade OR Re-transplantation, OR Death from respiratory failure.

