#### **12.1.9 Hospitalizations**

Hospitalizations for any reason other than a scheduled procedure should be regarded as serious adverse event and should be recorded in the eCRFs with admission date, discharge date, reason for admission, and additional diagnoses. If a patient requires mechanical ventilation for any reason other than a planned surgical procedure, dates of mechanical ventilation, and reason for mechanical ventilation should be recorded separately. A Hospitalization Discharge Summary may be requested by the Medical Monitor and shared with the DMC and/or AC.

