### **13.3 Adjudication Committee (AC)**

An independent, blinded Adjudication Committee (AC) will be established to assess all events that meet the progression of BOS criteria in every patient. Details of the event review will be included in the AC's Charter.

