9.5 Handling of Missing Data

9.5.1 Handling of Missing Efficacy Data

If a patient prematurely discontinues clinical trial participation for any reason apart death, re-transplantation or withdrawal of consent, he/she will be encouraged to complete the follow-up. All observed available data will be used for the primary **CCI** analyses. The assumption of the LMM (section 14.1) for missing data will be MAR. Since the definition of progression of BOS

includes all relevant intercurrent events (IEs) as failures, drop-outs due to other reasons will be treated as non-informative censoring (section 14.3.2).

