14.1 PRIMARY EFFICACY ANALYSIS

14.1.1 Analysis Population and Estimand

The primary endpoints will be analyzed using a “composite strategy” (International Conference on Harmonization (ICH) guideline E9 addendum on estimands and sensitivity analysis in clinical trials to the guideline on statistical principles for clinical trials). The estimand is defined by the following:

- Population: adult recipients of a single pulmonary allograft with clinically defined BOS, matching the inclusion and exclusion protocol criteria.
- Variable: FEV₁ data at Week 48 (visit 9) collected from the on site **CCI** spirometer (data collected with the **CCI** home spirometer will be used for supplementary analyses). Only accepted over-reader best FEV₁ data for the session from **CCI** will be used for analysis; data will not be re-derived.
- Intercurrent events: After IEs such as stopping treatment with L-CsA, augmentation of SoC therapy, etc., FEV1 measurements will still be collected and used in the analysis. In case of IEs preventing the use of FEV1 measurements, i.e. death and re-transplantation, the FEV1 will be imputed as treatment failure: FEV1 equal to zero for all visits subsequent the event. Rejected spirometries are those that did not meet the American Thoracic Society criteria; if rejected, then they would be re-done but there may be cases where they are rejected twice and resulting in missing data. Rejected spirometry is not an indicator of a better/worse outcome and can be assumed to be MAR.

- Population-level summary: difference in mean change from baseline in the FEV₁ at week 48 between treatment groups.

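### SAP 8.5 gives the unblinded investigator the last word on BOS progression and so forgoes a blinded committee assessment of the same events

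*SAP*

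**What the plan says.** Protocol 13.3, repeated in the synopsis, sets up the committee: "An independent, blinded Adjudication Committee (AC) will be established to assess all events that meet the progression of BOS criteria in every patient". It leaves the details to the AC charter, which is not among the documents, and does not say whether the committee or the investigator prevails.

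SAP 8.5 describes three independent physicians who review progression data under blind after each patient has finished the study, so that recording is consistent and complete. It then deals with disagreement: "In case there are discrepancies between the assessment of the AC and that of the investigator regarding BOS progression events", the CRO informs the investigator. The section closes with: "In all cases, the final decision as to whether or not specific event qualifies as BOS progression stands with the Investigator".

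The trial is open-label. Protocol 9.3.1 says: "Clinical trial monitors, treating physicians, study nurses, study coordinators, and enrolled patients will not be blinded to treatment assignment". SAP 7.2 adds that the investigator learns each patient's assignment through the eCRF.

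Protocol 12.1.2 defines progression as a confirmed spirometric decline, and then continues: "OR worsening in BOS Severity grade OR Re-transplantation, OR Death from respiratory failure".

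**The concern.** When the AC and the investigator disagree, two classifications of the same event exist: one made under blind, and one made by someone who knows the arm. The SAP lets the second stand. Because AC review follows the patient's study period, the investigator can settle a disputed event knowing both the arm and the patient's full course.

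What is at stake is the credibility of the time-to-progression results: the Kaplan-Meier event-free rates described in SAP 8.1 and the log-rank comparisons by subgroup in SAP 14.5. These are descriptive, but they will still be read as evidence about the drug. Under Protocol 15 the final SAP defines the analysis of record, so the rule in 8.5 matters unless a later section overrides it.

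**Working it through.** The plan gives no figure on this point, so there is none to reproduce. The check has two parts.

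**1. Where can the two assessments differ?** Taking the components of Protocol 12.1.2 in turn:

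- *Spirometric decline.* Numeric thresholds, confirmed by measurements at least 2 weeks apart. Spirometry is done by blinded staff (Protocol 9.3.1) and read centrally under blind (Protocol 9.2). Little room for judgement.
- *Grade worsening.* Grades are FEV1 bands (Protocol Tables 1 and 3). Little room.
- *Re-transplantation.* A dated fact.
- *Death from respiratory failure.* Needs a judgement of cause, so this is the likeliest place for disagreement.

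Even the last may be closed. SAP 9.5.1 says the progression definition "includes all relevant intercurrent events (IEs) as failures", and SAP 14.1.1 names the relevant events for FEV1: "In case of IEs preventing the use of FEV1 measurements, i.e. death and re-transplantation". If SAP 14.3.2, which is redacted, counts every death as a failure, cause of death no longer matters. The readable text does not settle this, nor whether AC or investigator status is analysed.

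**2. How much does one changed event move the result?** This is an illustration only.

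Inputs: 62 randomized (SAP 8.2). Assumed, not in the documents: a 31/31 split, the event counts, and no censoring before the end of follow-up.

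- Shift in one arm's event-free proportion = 1/n. For n = 31: 1/31 = 3.2 points.
- SE of the between-arm difference = sqrt(2p(1−p)/n), with p = events/n in each arm. The 95% half-width is 1.96 × SE.

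| n per arm | events per arm | shift (points) | SE (points) | 95% half-width | shift/SE |
|---|---|---|---|---|---|
| 31 | 9 | 3.2 | 11.5 | 22.6 | 0.28 |
| 31 | 12 | 3.2 | 12.4 | 24.2 | 0.26 |
| 31 | 16 | 3.2 | 12.7 | 24.9 | 0.25 |

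Subgroups: SAP 14.5 says levels may be pooled to reach at least 10 patients per stratum. That is a pooling target, not a guaranteed minimum, and the text does not say whether it applies per arm. With 10 per arm, one event moves the proportion by 1/10 = 10 points (0.45 to 0.49 SE at 3 to 5 events per arm). With 5 per arm it moves by 1/5 = 20 points (0.65 to 0.79 SE at 1 to 3 events per arm).

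Log-rank statistic: simulated with exponential times, no true difference, and one randomly chosen event in one arm reclassified as event-free (4,000 runs per cell). Mean absolute change in z at 30%, 40% and 50% progression:

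- 31 per arm: 0.28, 0.26, 0.25
- 10 per arm: 0.53, 0.47, 0.45
- 5 per arm: about 0.74, 0.68, 0.64

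No direction is presumed, and equal changes in both arms tend to cancel.

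**The case against.** The strongest reply is that nothing visible has been taken away. The protocol never gives the AC authority to decide, and the SAP presents its work as a continuing data-quality role. A reader might infer that the SAP overturns or weakens a protocol safeguard. The documents do not support that: Protocol 13.3 is silent on whose call prevails, and the charter may say more. The protocol's own argument against open-label bias (9.2) rests on blinded spirometry and central reading, not on the AC. This part of the reply stands.

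A second reply is that exposure may be close to nil, since most components are numeric or dated and cause of death may not count. This largely stands as a limit on size. It does not show that disagreement will not happen; SAP 8.5 itself provides for it.

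A third is that the main time-to-progression analysis is redacted. This also stands: SAP 14.3.2 may already use AC status.

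A fourth is that a 1/n shift is true of any small trial and does not measure the effect of this rule. That is correct, because no disagreement rate is given. The arithmetic shows sensitivity to a single event, not expected bias.

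A reader might also infer an inflated type I error. That would need an assumed rate and direction of overrides, and there is no confirmatory claim here to inflate. The synopsis confines the testing hierarchy to the double-lung study, and SAP 14 makes all analyses in this study descriptive.

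**Conclusion.** The point holds in a limited form. As written, SAP 8.5 lets an unblinded decision set the status of disputed events although a blinded assessment of them is available. That is a weak choice in an open-label trial, but not a conflict with the protocol and not evidence that bias occurred.

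The effect is confined to disputed events in descriptive time-to-progression results. In the full sample one such event is small against the uncertainty: 3.2 points against 95% limits of roughly ±23 to 25 points, under the assumed split, event counts and absence of early censoring. In small subgroups it is more visible. The primary FEV1 analysis does not depend on it. Severity is low; the reason to act is that acting is cheap.

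**What to change.** Amend SAP 8.5 before database lock:

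- Time-to-progression analyses, including the log-rank comparisons in 14.5, use the event status given by the AC under blind.
- The event date is the recorded date of the spirometry, re-transplantation or death, unless the AC charter already has the AC assign dates. No readable section says that it does.
- Investigator status is used in a sensitivity analysis.
- AC–investigator disagreements are tabulated by arm and by component (spirometric decline, grade, re-transplantation, death).

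If the sponsor prefers to keep investigator status as the main definition because the change comes late, pre-specify the AC-status analysis as the sensitivity analysis, with the same table. If SAP 14.3.2 already uses AC status, only 8.5 needs correcting.

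The cost is mainly wording. No new readers are needed, and because AC review follows each patient's study period, patient care is unaffected. The downsides are:

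- Final event status waits for AC close-out.
- The AC charter may need aligning.
- Randomization has ended, so the change must be documented as made without knowledge of results by arm.
- Treatment details must be masked in hospital records sent to the committee, since Protocol 12.1.9 says: "A Hospitalization Discharge Summary may be requested by the Medical Monitor and shared with the DMC and/or AC".
- AC status does not remove any influence of the known arm on whether or when confirmatory spirometry is done.
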